3.1 Administration Schedule

All patients will receive trametinib 2mg daily continuously until intolerable toxicity, disease progression, or the end of the study.

Trametinib should be administered once per day, continuously; and should be taken at about the same time each day. The study drug should be administered together with approximately eight ounces of water. Trametinib should be taken fasting, at least 1 hour before or 2 hours after a meal. If a subject vomits after taking study medication, the subject should be instructed not to retake the dose and should take the next scheduled dose.

If a dose of trametinib is missed, only take the dose if it is more than 12 hours until the next scheduled dose.

Trametinib should be stored at 2-8°C (36-46°F). Refrigerate. Do not freeze.

3.2 Adverse Event Reporting Requirements

The Adverse Event Reporting Requirements for all EAY131 subprotocols are outlined in the MATCH MASTER protocol. Please refer to those guidelines when determining if an event qualifies as a Serious Adverse Event (SAE) and requires expedited reporting via CTEP's Adverse Event Reporting System (CTEP-AERS).

In addition, the following section outlines agent specific requirements and must be followed to ensure all reporting requirements are met.

Rev. 12/16

3.2.1 Additional instructions, requirements and exceptions for EAY131-Subprotocol S1.

Additional Instructions

For instructions on how to specifically report events that result in persistent or significant disability/incapacity, congenital anomaly, or birth defect events via CTEP-AERS, please contact the AEMD Help Desk at [contact] or [contact]. This will need to be discussed on a case-by-case basis.

EAY131- Subprotocol S1 specific expedited reporting requirements:

- **LVEF Changes:** If any of the following circumstances occur, the event(s) must be reported via CTEP-AERS according to the timeframes outlined in the AE table in section 5.3.6 of the MATCH Master protocol
 - Asymptomatic: Absolute decrease of >10% in LVEF compared to baseline and ejection fraction below the institution's LLN and LVEF **does not recover** within 4 weeks
 - Symptomatic: Grade 3-4 LVEF

Please refer to the dose modification instructions for further information regarding Treatment Modification and Management Guidelines for LVEF Decrease

- **Visual Changes:** If RPED (retinal pigment epithelial detachments) or RVO (retinal vein occlusion) are diagnosed, the event(s) must be reported via CTEP-AERS according to the timeframes outlined in the AE table in Section 5.3.6 of the MATCH Master protocol. Please refer to the dose modification instructions for further information regarding Treatment Modification and Management Guidelines for Visual Changes.
- **Liver Chemistry Changes:** If any of the following circumstances occur, the event(s) must be reported via CTEP-AERS according to the timeframes outlined in the AE table in section 5.3.6 of the MATCH Master protocol
 - ALT \geq 3xULN **and** bilirubin \geq 2x ULN or $>$ 35% direct bilirubin
 - ALT \geq 3xULN **and** INR \geq 1.5, if INR measured (INR threshold does not apply if subject is on anticoagulant)
- Please refer to the dose modification instructions for further information regarding Treatment Modification and Management Guidelines for Liver Chemistry Changes
- **Pregnancies:** Pregnancies and suspected pregnancies (including a positive or inconclusive pregnancy test, regardless of age or disease state) occurring while the subject is on Trametinib, or within 28 days of the subject's last dose of Trametinib, are considered immediately reportable events. The pregnancy, suspected pregnancy, or positive/ inconclusive pregnancy test must be reported via CTEP-AERS within 24 hours of the Investigator's knowledge. Please refer to Appendix VIII in MATCH Master protocol for detailed instructions on how to report the occurrence of a pregnancy as well as the outcome of all pregnancies.

EAY131-S1 specific expedited reporting exceptions:

For study Subprotocol S1, the adverse events listed below **do not** require expedited reporting via CTEP-AERS:

- If an AE meets the reporting requirements of the protocol, and it is listed on the SPEER, it should **ONLY** be reported via CTEP-AERS if the grade being reported exceeds the grade listed in the parentheses next to the event

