D. Disease measurements are repeated every 2 cycles for the first 26 cycles, and every 3 cycles thereafter until PD or start of another MATCH treatment step. The baseline evaluation should be performed as closely as possible to the beginning of treatment and never more than 6 weeks before registration to treatment step. For multiple myeloma patients, please refer to Section 6.4 of the MATCH Master Protocol for additional information on myeloma response criteria and the required disease assessments. Documentation (radiologic) must be provided for patients removed from study for progressive disease.

Rev. 3/17
Rev. Add13

E. Additional blood specimens and/or biopsies are to be submitted from consenting patients per Section 9.3.2 of the MATCH Master Protocol. Submit at the following time points, as applicable:

- Blood specimens are to be submitted at the end of Cycle 2 (prior to start of Cycle 3 treatment). If patient progresses or treatment is discontinued prior to Cycle 3, collect the blood at that time instead. On-treatment kits for blood sample collections will be automatically shipped to sites upon registration to the treatment step.
- Screening biopsies for additional aMOI assessments after registration to appropriate screening step, if applicable (Step 2 or Step 4).
- At end of all MATCH study treatments, blood specimens and/or research biopsy after consent and registration to Step 8

Please refer to Section 4 of the MATCH Master Protocol to determine whether the patient proceeds to the next screening step or to follow-up (with a potential end of treatment biopsy for research purposes on Step 8). Samples are to be submitted as outlined in Section 9 of the MATCH Master Protocol. To order Step 2/4 Screening or Step 8 kits, complete the EAY131 Collection and Shipping Kit Order Form (See Appendix XII of the MATCH Master Protocol) and fax to [contact].

F. Every 3 months if patient is < 2 years from study entry, and every 6 months for year 3. Toxicity assessments and radiologic evaluations are not required to be done during Follow Up if progression has been previously reported; however if an adverse event occurs post treatment that meets the SAE reporting requirements, it still must be reported via CTEP-AERS, even if progression has occurred.

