5.1.10 Nursing/Patient Implications
Women of childbearing potential and men must agree to use adequate contraception (hormonal or barrier method of birth control; abstinence) prior to study entry, for the duration of study participation, and for 4 months after completion of study.

Rev. 12/16

6. Translational Studies

Please refer to the MATCH Master Protocol for information on the Translational Studies.

7. References

Balagula, Y., K. Barth Huston, K.J. Busam, et al. (2010). Dermatologic side effects associated with the MEK 1/2 inhibitor selumetinib (AZD6244, ARRY-142886). *Invest New Drugs*. 29:1114-1121.

Bekaii-Saab, T., M.A. Phelps, X. Li, et al. (2011). Multi-institutional phase II study of selumetinib in patients with metastatic biliary cancers. *J Clin Oncol*. 29:2357-2363.

Bendell, J., P. LoRusso, E. Kwak, et al. (2011). Clinical combination of the MEK inhibitor GDC-0973 and the PI3K inhibitor GDC-0941: A first-in-human phase Ib study in patients with advanced solid tumors. *AACR Meeting Abstracts*. Abstract LB-89.

Blumenschein, G.R., E.F. Smit, D. Planchard, et al. (2013). MEK114653: A randomized, multicenter, phase II study to assess efficacy and safety of trametinib (T) compared with docetaxel (D) in KRAS-mutant advanced non-small cell lung cancer (NSCLC). *J Clin Oncol*. 31:Abstract 8029.

Borthakur, G., J.M. Foran, T. Kadia, et al. (2010). GSK1120212, a MEK1/MEK2 inhibitor, demonstrates acceptable tolerability and preliminary activity in a dose rising trial in subjects with AML and other hematologic malignancies. *Blood (ASH Annual Meeting Abstracts)*. 116:Abstract 3281.

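### Within this subprotocol, pregnancy reporting stops 28 days after the last dose, which covers about a quarter of a 4-month contraception period that starts from a different, undefined point

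*Protocol*

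**What the plan says.** Section 3.2.1, among the expedited reporting requirements specific to this subprotocol, says that pregnancies and suspected pregnancies on trametinib or "within 28 days of the subject's last dose of Trametinib" are immediately reportable. They "must be reported via CTEP-AERS within 24 hours of the Investigator's knowledge". For procedure the section points elsewhere: "Please refer to Appendix VIII in MATCH Master protocol for detailed instructions on how to report the occurrence of a pregnancy", and the same appendix is cited for reporting outcomes.

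Section 5.1.10 sets the contraception undertaking. "Women of childbearing potential and men must agree to use adequate contraception" before entry, "for the duration of study participation, and for 4 months after completion of study".

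Two further statements bear on the point. Section 3.2 opens by saying "The Adverse Event Reporting Requirements for all EAY131 subprotocols are outlined in the MATCH MASTER protocol" and presents the subprotocol's own rules as additional to those. Footnote F to the calendar in Section 4.1 says that "if an adverse event occurs post treatment that meets the SAE reporting requirements, it still must be reported via CTEP-AERS", even after progression. It does not name pregnancy.

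**The concern.** The protocol asks patients to avoid conception for months after treatment, but its own trigger for reporting a pregnancy closes after four weeks. A site that learns of a pregnancy arising in the second, third or fourth month after the last dose finds no pregnancy rule in this document that calls for a report.

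The setting makes a clear rule more important. The calendar in Section 4.1 schedules the pregnancy test only before treatment, so later capture depends on sites hearing of a pregnancy and knowing that it must be reported. Follow-up contacts are every 3 months in the first two years. A contact about 3 months after the last dose falls after day 28 and, counted from the last dose, inside the 4 months.

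What is at stake is the completeness of safety data on possible fetal exposure. No efficacy estimate or decision rule depends on it.

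**Working it through.** The plan gives no figure for the overlap of the two periods, so there is none to reproduce. The check compares them directly.

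**Inputs**
- Reporting window after treatment: 28 days from the last dose (Section 3.2.1).
- Contraception period after the study: 4 months from completion of study (Section 5.1.10).
- Length of a month: not stated. Taken as 28 days (one cycle), 30, 30.44 (calendar average) or 31.
- Effective half-life: about 4.5 days (Section 1.1.2), for context only.

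**Step 1: both periods counted from the last dose.** This reading favours the protocol most. Covered share = 28 / (4 × month length). Uncovered days = 4 × month length − 28.

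| Month length (days) | 4 months (days) | Uncovered (days) | Covered | Uncovered |
|---|---|---|---|---|
| 28 | 112 | 84 | 25.0% | 75.0% |
| 30 | 120 | 92 | 23.3% | 76.7% |
| 30.44 | 121.8 | 93.8 | 23.0% | 77.0% |
| 31 | 124 | 96 | 22.6% | 77.4% |

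The choice of month hardly matters: the window covers 23% to 25% of the period.

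**Step 2: starting points as written.** Let L be the days from the last dose to completion of study. Contraception is required throughout participation and for 4 months beyond it, so it runs for L + 121.8 days after the last dose. The uncovered part is L + 121.8 − 28 = L + 93.8 days, which grows day for day with L. The document does not define study completion. Section 4.1 schedules follow-up into year 3, but nothing says whether follow-up counts towards L. The uncovered part is therefore at least about 94 days whenever L is zero or more, and no upper bound can be given.

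**Step 3: does another statement close the gap?**
- Footnote F in Section 4.1 covers post-treatment adverse events that meet the SAE criteria. Pregnancy is not mentioned.
- Section 3.2.1 tells sites whom to contact about congenital anomaly and birth defect events, with no 28-day limit. That concerns a later outcome, not the pregnancy itself.
- Master Protocol Appendix VIII is cited for how to report a pregnancy and its outcome, not for when a pregnancy becomes reportable.

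None of these sets a pregnancy trigger beyond day 28.

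**Step 4: pharmacokinetic context.** 28 / 4.5 = 6.2 half-lives, and 0.5^6.2 is about 0.013, so about 1.3% of the drug would remain at day 28.

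**The case against.** The strongest reply is that the subprotocol does not stand alone. Section 3.2 places its rules on top of the Master Protocol's reporting requirements, and those may already make later pregnancies reportable. This stands. A reader might infer that most of the contraception period has no reporting rule at all, or that such pregnancies would go uncaptured and unfollowed. The document does not support that, because the governing text is not at hand. What can be said is that this document supplies no trigger. It states 28 days among its agent-specific rules, so a site could reasonably take that as the limit.

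A second reply is that the two periods serve different purposes. One triggers a 24-hour report, the other is a precaution for patients, and a site can comply with both. This also stands: they need not be equal, and the sections do not contradict each other in the strict sense. But the document does not say that the difference is intended.

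Third, 28 days is about six half-lives, so a pharmacokinetic reason for the shorter window is possible. The protocol does not offer it. The calculation does limit what the percentages mean: they measure calendar time, not exposure or risk.

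Fourth, a reader might infer that a pregnancy in months 2 to 4 is itself a breach of the protocol. It is not. Section 5.1.10 requires agreement to use contraception, and contraception can fail without any breach.

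Finally, serious outcomes are not plainly without a route, given the birth defect instruction and footnote F. That softens the consequence but leaves the pregnancy trigger where it is.

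**Conclusion.** The point holds for this subprotocol. Its pregnancy-reporting window covers about a quarter of the contraception period on the most favourable reading (28 of about 122 days, with 84 to 96 days uncovered depending on the month length assumed), and less if study completion falls after the last dose. The starting points differ, one of them is undefined, and nothing shown explains or closes the gap.

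The conclusion assumes that the month lengths above are reasonable and that completion of study does not precede the last dose. It does not extend to the MATCH programme as a whole, since the Master Protocol may cover later pregnancies. If it does, the 28 days stated here could still mislead sites, and a cross-reference would be needed.

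The document gives no pregnancy rate, so the number of reports that might be missed cannot be estimated. This is a low-cost improvement to safety reporting.

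**What to change.** In Section 3.2.1, extend the pregnancy-reporting window to the end of whatever contraception period Section 5.1.10 sets. Reconcile the two sections in length and starting point, with each other and with Master Protocol Appendix VIII, and define completion of study if it remains a starting point. If the sponsor means the periods to differ, say so in both sections and give the reason.

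The length and starting point of the contraception period are left to the sponsor. In particular, simply moving its start to the last dose would not be a neutral edit: it could shorten the period for any patient whose study completion falls later.

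The cost is about one sentence in each section and a few additional CTEP-AERS reports. No efficacy analysis changes.

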3.2.2 Second Primary Cancer Reporting Requirements

NOTE: The MATCH Master Protocol outlines the standard requirements for the reporting of second primaries. Please be aware that there are additional requirements

for this subprotocol. Please adhere to the guidelines outlined below for the reporting of second primaries on this subprotocol.

All cases of second (second malignancy is a cancer that is unrelated to any prior anti-cancer treatment, including the treatment on this protocol) **and** secondary malignancies (secondary malignancy is a cancer caused by any prior anti-cancer treatment, including the treatment on this protocol), including acute myeloid leukemia (AML) and myelodysplastic syndrome (MDS)], regardless of attribution, that occur following treatment on NCI-sponsored trials must be reported as follows:

1. Complete a Second Primary Form in Medidata Rave within 14 days.
2. Report the diagnosis via CTEP-AERS, regardless of attribution, at <http://ctep.cancer.gov>
Report under a.) *leukemia secondary to oncology chemotherapy*, b.) *myelodysplastic syndrome*, or c.) *treatment related secondary malignancy*
3. Upload a copy of the pathology report to ECOG-ACRIN via Medidata Rave and submit a copy to NCI/CTEP confirming the diagnosis.
4. If the patient has been diagnosed with AML/MDS, upload a copy of the cytogenetics report (if available) to ECOG-ACRIN via Medidata Rave and submit a copy to NCI/CTEP.

NOTE: **All new malignant tumors must be reported through CTEP-AERS whether or not they are thought to be related to either previous or current treatment.** All new malignancies should be reported including solid tumors (including non-melanoma skin malignancies), hematologic malignancies, Myelodysplastic Syndrome (MDS)/Acute Myelogenous Leukemia (AML), and *in situ* tumors.

Whenever possible, the CTEP-AERS report should include the following:

- tumor pathology
- history of prior tumors
- prior treatment/current treatment including duration
- any associated risk factors or evidence regarding how long the tumor may have been present
- when and how the tumor was detected
- molecular characterization or cytogenetics or the original tumor (if available) and of any new tumor/treatment and outcome (if available).

NOTE: The Second Primary Form and the CTEP-AERS report should not be used to report recurrence or development of metastatic disease.

NOTE: If a patient has been enrolled in more than one NCI-sponsored study, the Second Primary Form must be submitted for the most recent trial. ECOG-ACRIN must be provided with a copy of the form and the associated pathology report and cytogenetics report (if available) even if ECOG-ACRIN was not the patient's most recent trial.

NOTE: Once data regarding survival and remission status are no longer required by the protocol, no follow-up data should be submitted via CTEP-AERS or by the Second Primary Form.

Rev. 1/17
Rev. Add19

3.3 Comprehensive Adverse Events and Potential Risks List (CAEPR) for Trametinib dimethyl sulfoxide (GSK1120212B, NSC 763093)

The Comprehensive Adverse Events and Potential Risks list (CAEPR) provides a single list of reported and/or potential adverse events (AE) associated with an agent using a uniform presentation of events by body system. In addition to the comprehensive list, a subset, the Specific Protocol Exceptions to Expedited Reporting (SPEER), appears in a separate column and is identified with bold and italicized text. This subset of AEs (SPEER) is a list of events that are protocol specific exceptions to expedited reporting to NCI (except as noted below). Refer to the 'CTEP, NCI Guidelines: Adverse Event Reporting Requirements' http://ctep.cancer.gov/protocolDevelopment/electronic_applications/docs/aeguide_lines.pdf for further clarification. Frequency is provided based on 1111 patients. Below is the CAEPR for Trametinib dimethyl sulfoxide (GSK1120212B).

NOTE: If an AE meets the reporting requirements of the protocol, and it is listed on the SPEER, it should ONLY be reported via CTEP-AERS if the grade being reported exceeds the grade listed in the parentheses next to the event.

Version 2.5, February 1, 2019¹

Adverse Events with Possible Relationship to Trametinib (GSK1120212B) (CTCAE 5.0 Term) [n= 1111]			Specific Protocol Exceptions to Expedited Reporting (SPEER)
Likely (>20%)	Less Likely (<=20%)	Rare but Serious (<3%)	
BLOOD AND LYMPHATIC SYSTEM DISORDERS			
	Anemia		Anemia (Gr 3)
CARDIAC DISORDERS			
		Heart failure	
		Left ventricular systolic dysfunction	
	Sinus bradycardia		
EYE DISORDERS			
	Blurred vision		
	Dry eye		
		Eye disorders - Other (chorioretinopathy also known as retinal pigment epithelial detachment)	
		Eye disorders - Other (retinal vein occlusion)	
	Eye disorders - Other (visual disorders) ²		
		Papilledema	
	Periorbital edema		
GASTROINTESTINAL DISORDERS			
	Abdominal pain		Abdominal pain (Gr 2)
		Colitis	
		Colonic perforation	
	Constipation		Constipation (Gr 2)
Diarrhea			Diarrhea (Gr 3)

Adverse Events with Possible Relationship to Trametinib (GSK1120212B) (CTCAE 5.0 Term) [n= 1111]			Specific Protocol Exceptions to Expedited Reporting (SPEER)
Likely (>20%)	Less Likely (<=20%)	Rare but Serious (<3%)	
	Dry mouth		Dry mouth (Gr 2)
	Dyspepsia		Dyspepsia (Gr 2)
	Mucositis oral		Mucositis oral (Gr 3)
Nausea			Nausea (Gr 3)
	Vomiting		Vomiting (Gr 3)
GENERAL DISORDERS AND ADMINISTRATION SITE CONDITIONS			
	Chills		Chills (Gr 2)
	Edema face		
Fatigue			Fatigue (Gr 3)
	Fever		Fever (Gr 2)
Generalized edema ³			Generalized edema³ (Gr 2)
IMMUNE SYSTEM DISORDERS			
	Allergic reaction ⁴		
INFECTIONS AND INFESTATIONS			
	Folliculitis		Folliculitis (Gr 2)
	Lung infection		
	Paronychia		Paronychia (Gr 2)
	Skin infection		Skin infection (Gr 2)
INVESTIGATIONS			
	Alanine aminotransferase increased		Alanine aminotransferase increased (Gr 3)
	Alkaline phosphatase increased		Alkaline phosphatase increased (Gr 2)
	Aspartate aminotransferase increased		Aspartate aminotransferase increased (Gr 3)
	CPK increased		
	Ejection fraction decreased		
METABOLISM AND NUTRITION DISORDERS			
	Anorexia		Anorexia (Gr 3)
	Dehydration		Dehydration (Gr 3)
	Hypoalbuminemia		
	Hypomagnesemia		Hypomagnesemia (Gr 2)
	Hyponatremia		Hyponatremia (Gr 3)
MUSCULOSKELETAL AND CONNECTIVE TISSUE DISORDERS			
	Arthralgia		
	Back pain		Back pain (Gr 2)
	Pain in extremity		Pain in extremity (Gr 2)
		Rhabdomyolysis	
NERVOUS SYSTEM DISORDERS			
	Dizziness		Dizziness (Gr 2)
	Headache		Headache (Gr 2)

Adverse Events with Possible Relationship to Trametinib (GSK1120212B) (CTCAE 5.0 Term) [n= 1111]			Specific Protocol Exceptions to Expedited Reporting (SPEER)
Likely (>20%)	Less Likely (<=20%)	Rare but Serious (<3%)	
RESPIRATORY, THORACIC AND MEDIASTINAL DISORDERS			
	Cough		Cough (Gr 2)
	Dyspnea		Dyspnea (Gr 3)
		Pneumonitis	
SKIN AND SUBCUTANEOUS TISSUE DISORDERS			
	Alopecia		Alopecia (Gr 2)
	Dry skin		Dry skin (Gr 2)
	Nail changes		
		Palmar-plantar erythrodysesthesia syndrome	
	Pruritus		Pruritus (Gr 2)
Skin and subcutaneous tissue disorders - Other (rash) ⁵			Skin and subcutaneous tissue disorders - Other (rash)⁵ (Gr 3)
VASCULAR DISORDERS			
	Hypertension		Hypertension (Gr 3)
		Thromboembolic event (venous)	
	Vascular disorders - Other (hemorrhage) ⁶		

¹This table will be updated as the toxicity profile of the agent is revised. Updates will be distributed to all Principal Investigators at the time of revision. The current version can be obtained by contacting [contact]. Your name, the name of the investigator, the protocol and the agent should be included in the e-mail.

²Visual disorders include visual disturbance that can be associated with conjunctival hemorrhage, corneal graft rejection, cyclitis, eye nevus, halo vision, iritis, macular edema, retinal hemorrhage, visual acuity reduced, visual impairment, and vitreous detachment.

³Generalized edema includes edema, lymphedema, and edema limbs.

⁴Hypersensitivity (allergic reactions) may present with symptoms such as fever, rash, increased liver function tests, and visual disturbances.

⁵Skin and subcutaneous tissue disorders - Other (rash) may include rash, rosacea, erythematous rash, genital rash, rash macular, exfoliative rash, rash generalized, erythema, rash papular, seborrhoeic dermatitis, dermatitis psoriasiform, rash follicular, skin fissures, and skin chapped.

⁶The majority of hemorrhage events were mild. Major events, defined as symptomatic bleeding in a critical area or organ (e.g., eye, GI hemorrhage, GU hemorrhage, respiratory hemorrhage), and fatal intracranial hemorrhages have been reported.

Adverse events reported on trametinib dimethyl sulfoxide (GSK1120212B) trials, but for which there is insufficient evidence to suggest that there was a reasonable possibility that trametinib dimethyl sulfoxide (GSK1120212B) caused the adverse event:

BLOOD AND LYMPHATIC SYSTEM DISORDERS - Disseminated intravascular coagulation; Febrile neutropenia; Leukocytosis

CARDIAC DISORDERS - Atrial fibrillation; Cardiac arrest; Myocardial infarction; Restrictive cardiomyopathy; Sinus tachycardia

EYE DISORDERS - Corneal ulcer; Eyelid function disorder; Flashing lights; Floaters; Glaucoma; Photophobia

GASTROINTESTINAL DISORDERS - Ascites; Duodenal ulcer; Esophageal necrosis; Esophageal ulcer; Esophagitis; Gastric hemorrhage; Gastric ulcer; Gastritis; Gastrointestinal disorders - Other (intestinal obstruction); Gastrointestinal disorders - Other (pneumatosis intestinalis); Gastrointestinal fistula; Gingival pain; Hemorrhoidal hemorrhage; Ileus; Obstruction gastric; Pancreatitis; Small intestinal obstruction

GENERAL DISORDERS AND ADMINISTRATION SITE CONDITIONS - Flu like symptoms; General disorders and administration site conditions - Other (axillary pain); Localized edema; Malaise; Non-cardiac chest pain; Pain

HEPATOBILIARY DISORDERS - Cholecystitis; Hepatic failure; Hepatic pain; Hepatobiliary disorders - Other (hepatic encephalopathy)

INFECTIONS AND INFESTATIONS - Biliary tract infection; Catheter related infection; Device related infection; Endocarditis infective; Enterocolitis infectious; Hepatitis viral; Infections and infestations - Other (abscess limb); Infections and infestations - Other (necrotizing fasciitis); Infections and infestations - Other (oral infection); Pharyngitis; Sepsis; Upper respiratory infection; Urinary tract infection

INJURY, POISONING AND PROCEDURAL COMPLICATIONS - Bruising

INVESTIGATIONS - Blood bilirubin increased; Blood lactate dehydrogenase increased; Creatinine increased; Electrocardiogram QT corrected interval prolonged; GGT increased; Lipase increased; Lymphocyte count decreased; Platelet count decreased; Serum amylase increased; White blood cell decreased

METABOLISM AND NUTRITION DISORDERS - Hyperglycemia; Hyperkalemia; Hyperphosphatemia; Hyperuricemia; Hypocalcemia; Hypoglycemia; Hypokalemia

MUSCULOSKELETAL AND CONNECTIVE TISSUE DISORDERS - Generalized muscle weakness; Muscle cramp; Musculoskeletal and connective tissue disorder - Other (compression fracture); Myalgia; Neck pain

NEOPLASMS BENIGN, MALIGNANT AND UNSPECIFIED (INCL CYSTS AND POLYPS) - Tumor hemorrhage; Tumor pain

NERVOUS SYSTEM DISORDERS - Dysgeusia; Encephalopathy; Intracranial hemorrhage; Lethargy; Nervous system disorders - Other (diplopia); Seizure; Somnolence; Stroke; Syncope; Transient ischemic attacks

PSYCHIATRIC DISORDERS - Anxiety; Confusion; Delirium; Depression; Hallucinations; Insomnia; Personality change

RENAL AND URINARY DISORDERS - Acute kidney injury; Cystitis noninfective; Dysuria; Hematuria; Proteinuria; Urinary incontinence

REPRODUCTIVE SYSTEM AND BREAST DISORDERS - Vaginal fistula; Vaginal hemorrhage

RESPIRATORY, THORACIC AND MEDIASTINAL DISORDERS - Bronchopulmonary hemorrhage; Hypoxia; Laryngeal edema; Oropharyngeal pain; Pleural effusion; Pneumothorax; Productive cough; Pulmonary hypertension; Respiratory failure; Sinus disorder

SKIN AND SUBCUTANEOUS TISSUE DISORDERS - Bullous dermatitis; Photosensitivity; Purpura; Skin and subcutaneous tissue disorders - Other (erythema nodosum); Skin ulceration; Urticaria

VASCULAR DISORDERS - Hematoma; Hot flashes; Hypotension

NOTE: Trametinib (GSK1120212B) in combination with other agents could cause an exacerbation of any adverse event currently known to be caused by the other agent, or the combination may result in events never previously associated with either agent.

Rev. 12/16

